Range of motion (ROM) or motion arc in this study will be measured using a universal goniometer following standardized procedures to ensure accuracy and reproducibility. Each joint will be assessed in a consistent anatomical position—either supine, seated, or standing—depending on the specific joint involved (e.g., seated for elbow, supine for knee). The Principal Investigator or Sub-Investigator will perform three consecutive measurements for each motion (e.g., flexion, extension), and the average value will be recorded. Key movements assessed will include knee flexion-extension, ankle dorsiflexion-plantarflexion, elbow flexion-extension, and lumbar spine flexion or fingertip-to-floor distance for back pain. The same assessor will conduct all measurements at each time point to minimize inter-rater variability. Any limitations due to pain, guarding, or compensatory movements will be noted. ROM data will be recorded on standardized forms and used to evaluate treatment effectiveness by comparing baseline to post-treatment values against established minimal clinically important difference (MCID) thresholds.

In this study, the minimal clinically important difference (MCID) for joint range of motion (ROM) will be used to define clinically meaningful improvements in mobility following treatment. Based on validated references, the MCID values applied are $\geq 10^\circ$ for knee flexion/extension (Mizner et al., 2005) and elbow flexion-extension arc (Picha et al., 2020), $\geq 5^\circ$ for ankle dorsiflexion/plantarflexion (Cleland et al., 2013), and either $\geq 10\%$ change or ≥ 5 cm improvement for lumbar spine mobility, depending on the measurement method used (Stratford et al., 1994). These thresholds represent the minimum degree of change perceived as beneficial by patients and are appropriate benchmarks for evaluating functional recovery in musculoskeletal pain conditions.

- 3) Assessment to investigate scales on thermal sensation, thermal comfort, and thermal acceptance using ASHRAE 7-point scale questionnaire and completed with time starting the thermal sensation.

Definition:

Thermal comfort is the condition of mind that expresses satisfaction with the thermal environment and is assessed by subjective evaluation.

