7.9.2 Secondary Endpoint

The assessment of secondary endpoints will be assessed through :

- Form 3 : Pemeriksaan nyeri awal pasien
- Form 4 : Pemeriksaan indikator rasa nyeri non verbal
- Form 5 : Pemeriksaan rentang gerak
- Form 6 : Pemeriksaan kekuatan otot

By Principal Investigator or Sub Investigator on 1st Visit, 2nd Visit and 3rd Visit.

- Form 8 : thermal sensation, thermal comfort, and thermal acceptance and time of thermal sensation.

By Participant on 1st Visit, 2nd Visit and 3rd Visit.

- Adverse events symptoms, concomitant medication, rescue medication that will be described in the Diary Participant.

By Participant on Day 0 until study is completed.

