7.4.2 Statistical Analysis Plan

The statistical analysis will be performed after data finalization and database lock, following the predefined analysis sets (PPS, FAS, and Safety Analysis Set). All analyses will be conducted using standard statistical software (e.g., SPSS, SAS, or R), with the level of statistical significance set at $p < 0.05$, unless otherwise adjusted.

Efficacy Analysis

- **Primary Endpoint (Pain Score using Brief Pain Inventory):**
 - **Test: Analysis of Covariance (ANCOVA)** adjusting for baseline BPI score

- **Equivalence testing:** Pairwise comparisons using **two one-sided t-tests (TOST)** to assess whether the difference in mean change from baseline falls within the equivalence margin (± 1.0)
- **Assumptions:** Normality and homogeneity of variance will be checked. If violated, non-parametric equivalent (e.g., **Wilcoxon rank-sum test**) will be used.
- **Secondary Endpoints:**
 - **Range of Motion (ROM) and Muscle Strength:**
 - **Test:** Repeated Measures ANOVA or mixed-effects model, depending on data completeness and correlation structure
 - If non-normal: **Friedman test** or **Wilcoxon signed-rank test** for within-group, **Kruskal-Wallis test** for between-group comparisons.
 - **Thermal Sensation, Comfort, and Acceptance (ASHRAE Scale):**
 - **Test:** Chi-square test or Fisher's exact test for categorical comparisons
 - **Ordinal regression** may be used to explore patterns of thermal perception across groups.
 - **Responding Analysis (pain reduction ≥ 3 points):**
 - **Test:** Chi-square test for group-wise comparison of response rates
 - **Risk difference** and **number needed to treat (NNT)** will be calculated.

Safety Analysis

- **Adverse Events (AEs) and Adverse Drug Reactions (ADRs):**
 - **Test:** Chi-square test or Fisher's exact test for comparing incidence across groups
 - Descriptive statistics for type, severity, onset, and duration
 - **Severity grading** and **causality assessment** using **Naranjo's algorithm**.
- **Rescue Medication Use:**
 - **Test:** Poisson regression or negative binomial regression if data are overdispersed
 - Summarized as a mean number of doses used per participant and compared between groups.

Demographic and Baseline Characteristics

- **Continuous Variables** (e.g., age, BMI):
 - **Test:** One-way ANOVA or **Kruskal-Wallis test** (if non-normal distribution)
- **Categorical Variables** (e.g., sex, diagnosis):
 - **Test:** Chi-square test or Fisher's exact test as appropriate

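### ROM and muscle strength are measured before treatment, but the protocol names no baseline adjustment and no treatment contrast for them; a baseline-adjusted Visit 3 comparison would be sharper at no cost

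*Protocol*

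**What the plan says.** Protocol Section 7.4.2 (under 7.10) sets the model for ROM and muscle strength as "Repeated Measures ANOVA or mixed-effects model, depending on data completeness and correlation structure". If the data are non-normal, it moves to Friedman or signed-rank tests within groups and to the "Kruskal-Wallis test for between-group comparisons". It does not state which visits are outcomes, whether the treatment test is the group effect or the group-by-visit term, whether the baseline value is a covariate, or whether Kruskal-Wallis is applied to raw values or to changes.

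The same section gives the primary endpoint an ANCOVA "adjusting for baseline BPI score".

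Section 7.9.2 has the ROM and strength forms completed "By Principal Investigator or Sub Investigator on 1st Visit, 2nd Visit and 3rd Visit". In the Day 0 flow of Section 7.7.2 these forms come at step 5, and randomization and first application come at step 7. The first value is therefore a true pre-treatment baseline.

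Section 5.2 says that ROM effectiveness is judged by "comparing baseline to post-treatment values against established minimal clinically important difference (MCID) thresholds".

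**The concern.** A baseline value is collected for both measures and is used for pain, but no use is named for it in the between-gel comparison of ROM and strength. The named model family admits tests that answer different questions. A group main effect over all three visits averages Day 0, where no treatment effect can exist, with Days 3 and 6, and it carries the full between-patient variance. A group-by-visit test uses Day 0 as the reference but spreads the question over 4 degrees of freedom. Adjusting for baseline removes most between-patient variance and can be aimed at the end of treatment.

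The trial aims to show that the gels perform alike. If ROM or strength is reported as not significantly different, the reader needs to know whether the test could have found a difference. As written, two analysts could both follow Section 7.4.2 and run tests of very different sensitivity on the same data. The choice between ANOVA and mixed model is also tied to features known only from the data.

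**Working it through.** **What the protocol supplies.** It gives no power, SD, effect size or visit correlation for ROM or strength, so there is no planned figure to reproduce. From the protocol come three arms, three visits, a 0.05 significance level (Section 7.4.2) and 54 evaluable per arm (Section 6.7; 60 enrolled). The arithmetic leading to 54 does not follow, since 2.39 + 0.84 = 3.23 and (3.23 × 1.81)² = 34.2. That is a separate matter; 54 is used here only as the planned evaluable number.

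**Assumed.** One arm differs from the other two by 0, 0.25 and 0.5 SD at Visits 1, 2 and 3. The SD is 1 at every visit and the correlation ρ is equal between visits. All data are on one common scale.

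**Formulas.** With one arm of three differing by d, the squared deviations of the arm means sum to (2/3)d², so the multiplier is 54 × 2/3 = 36. Power comes from the noncentral F distribution with these noncentralities:

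- Group main effect over three visits: the mean effect is (0 + 0.25 + 0.5)/3 = 0.25 and the variance of a patient's mean is (1 + 2ρ)/3. λ = 36 × 0.0625 × 3/(1 + 2ρ) = 6.75/(1 + 2ρ), with 2 and 159 df.
- Group-by-visit: the centred profile is (−0.25, 0, 0.25), with sum of squares 0.125. λ = 36 × 0.125/(1 − ρ) = 4.5/(1 − ρ), with 4 and 318 df.
- Baseline-adjusted Visit 3: the residual variance is 1 − ρ². λ = 36 × 0.25/(1 − ρ²) = 9/(1 − ρ²), with 2 and 158 df.

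At ρ = 0.5 these give λ = 3.38, 9.00 and 12.00.

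| ρ | Main effect | Group-by-visit | Baseline-adjusted Visit 3 |
|---|---|---|---|
| 0.3 | 43% | 49% | 80% |
| 0.5 | 35% | 66% | 88% |
| 0.6 | 32% | 77% | 92% |
| 0.7 | 30% | 89% | 97% |
| 0.8 | 28% | 98% | almost 100% |
| 0.9 | 26% | almost 100% | almost 100% |

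Simulation (2000 trials per setting) agrees. At ρ = 0.5, 0.6 and 0.7 it gives 37, 33 and 30% for the main effect, 67, 75 and 89% for group-by-visit, and 87, 92 and 97% for the adjusted comparison. At 60 per arm the formulas give, for ρ = 0.5 to 0.7, 39 to 33%, 71 to 92% and 91 to 98%.

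**Why the gap closes.** The ratio of adjusted to group-by-visit noncentrality is [9/(1 − ρ²)]/[4.5/(1 − ρ)] = 2/(1 + ρ), which is 1.33 at ρ = 0.5 and 1.05 at ρ = 0.9. What then remains is the cost of 4 rather than 2 numerator degrees of freedom, which matters little when both tests are near full power.

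**Other effect profile.** Let the effect appear in full at Visit 2 and persist, with its size set so that ANCOVA on the mean of the two post-baseline visits has 80% power. At ρ = 0.3, 0.5, 0.7, 0.8 and 0.9 the powers are:

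- main effect: 46, 34, 22, 16 and 10%
- group-by-visit: 41, 50, 59, 63 and 67%
- baseline-adjusted Visit 3: 58, 62, 64, 65 and 66%

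Again the main effect is weak throughout, and the gap between the other two closes as ρ rises.

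**Non-normal fallback.** Under the first profile, taking relative efficiency 0.955 (normal data), Kruskal-Wallis on raw Visit 3 values has about 74% power at any ρ. On change from baseline it has about 74, 84 and 93% at ρ = 0.5, 0.6 and 0.7. Which of the two is meant is not stated.

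**The case against.** The strongest reply is that the protocol never commits to the weak test. A reader might infer that all three visits enter as outcomes and that the treatment test therefore includes the pre-treatment visit and loses most of its power. Section 7.4.2 says neither. The visit schedule in Section 7.9.2 describes data collection, not a model. The mixed-effects option could carry baseline as a covariate, and Section 5.2 points to change from baseline, which is the group-by-visit term. This stands: the 30% to 37% figures describe a permitted reading, not the stated one.

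Three further replies also stand:

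- Kruskal-Wallis ignores baseline only if it is applied to raw values, and the text does not say that it is.
- The within-group tests are labelled as such, next to a separate test "for between-group comparisons". Including them is no error.
- The equivalence claim rests on the pain score with its ±1.0 margin. No margin or equivalence test is set for ROM or strength.

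It can also be said that covariates for a secondary endpoint belong in a separate SAP, which may exist. That limits the point but does not remove it. Section 7.4.2 is itself headed as the statistical analysis plan, does name the covariate for pain, and makes specific model choices for ROM and strength. A better choice using data already collected can be written there now.

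**Conclusion.** The point holds as an improvement to two secondary endpoints. Section 7.4.2 names neither a baseline adjustment nor a treatment contrast for ROM and strength, although the baseline is measured and the primary endpoint uses its own.

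On the reading closest to Section 5.2, the gain from adjusting is moderate: from about 67% to 87% power at correlation 0.5 and from 89% to 97% at 0.7, with almost nothing left to gain at 0.8 to 0.9. Only a main effect over all three visits would be badly underpowered, at about 30% to 37% for correlations of 0.5 to 0.7, and the text permits that reading without prescribing it.

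The figures rest on assumed effects, equal correlations, normal data, 54 per arm and overall three-arm tests. They also presuppose one common scale, whereas Section 5.2 lists "Key movements assessed will include knee flexion-extension, ankle dorsiflexion-plantarflexion, elbow flexion-extension" and lumbar mobility. How to combine those is a separate question. A reader might go further and infer that the primary equivalence conclusion is weakened; it is not affected.

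**What to change.** Replace the ROM and muscle strength entry in Section 7.4.2 with wording such as: ROM and muscle strength at Visits 2 and 3 will be analysed in a mixed model with the baseline value as covariate and with treatment, visit and treatment-by-visit as terms; the reported result is the baseline-adjusted difference at Visit 3, test gel minus each comparator, with its confidence interval. If the data are non-normal, estimate the same contrast on ranks with the baseline rank as covariate.

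This also settles the open choice between ANOVA and mixed model. The within-group tests may stay as description, with a sentence saying that they are not evidence comparing the gels.

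The cost is one paragraph, written before database lock. No new data, visits or participants are needed.

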Thermal sensation is assessed to determine whether a specific thermal condition can be considered comfortable or not. The most prominent scale used for the assessment of thermal sensation is the ASHRAE 7-point scale, which consists of seven verbal anchors: “cold”, “cool”, “slightly cool”, “neutral”, “slightly warm”, “warm”, and “hot”.

Thermal acceptance, refers to the degree to which a temperature range or condition is considered acceptable or tolerable by individuals.

The number of thermal sensations felt related to the product will be the result related to the participant's acceptance of the sensation.

- 4) Assessment to investigate the disappearance time of musculoskeletal pain (in days).

Definition:

To know the medication given is effective or not, we need to evaluate the musculoskeletal pain score. One of the result that can be seen is the disappearance time of musculoskeletal pain.

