7.8 CRITERIA AND PROCEDURE FOR DISCONTINUATION FOR PARTICIPANTS

7.8.1 Discontinuation Criteria

Investigator discontinues the study when a subject meets the following criteria.

1. When continuation of the study is difficult due to worsening of the target disease of this study or symptoms caused by the target disease
2. When a significant or persisting noncompliance with the protocol that makes it difficult to ensure safety or influences efficacy assessment was detected

3. When a subject is found not to meet the inclusion criteria for participants of this study or to meet the exclusion criteria
4. When it is difficult to continue the study or a subject requests for discontinuation due to onset of AEs
5. When a subject requests for discontinuation (not in relation to AEs)
6. When a subject stops visiting the site, making it difficult to continue the study
7. Other cases in which Investigator considers it difficult to continue the study

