7.8.2 Discontinuation Procedures

When any event corresponding to “Discontinuation Criteria” occurs during the study treatment, Investigator discontinues the administration of study drugs, performs the observation and tests specified in “ Schedule and Efficacy and Safety Endpoints,” and enter the results, discontinuation day, and reason for discontinuation in case report form.

Appropriate treatment including alternative therapies is provided after discontinuation.

When the study is discontinued due to occurrence of a safety problem in the subject concerned, appropriate measures are taken and the problem is addressed in accordance with “ Ensuring Safety of Participants.”

When a subject stops visiting the site, Investigator asks a subject to visit the site and efforts are made to perform the observation and tests specified in “Schedule, Efficacy and Safety Endpoints.”

If the designated observation and tests cannot be performed, Investigator promptly conducts follow-up investigation on the course after the latest observation and AEs over the phone, by letter, or other possible methods and enters the result in case report form. When confirmation was made with a person other than the subject for a compelling reason, the reason and the relationship of this person with the subject are entered in case report form.

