7.9.1 Primary Endpoint

The assessment of primary endpoint will be assessed through form 2, Inventerisasi Rasa Nyeri Singkat on 1st Visit, 2nd Visit and 3rd Visit.

The primary end-point is the difference BPI scale ≥ 3 , from initial scale of pain to the end of treatment will be captured as the primary efficacy endpoint.

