7.10 STATISTICAL ANALYSIS

7.4.1 Analysis Sets

In the efficacy analysis, the **Per Protocol Set (PPS)** will be used as the primary analysis set, while the **Full Analysis Set (FAS)** will serve as the secondary analysis set. For safety analysis, the **Safety Analysis Set** will be used. The definitions are as follows:

- **Per Protocol Set (PPS):**
The PPS includes participants who do not have any major protocol violations (such as not meeting inclusion/exclusion criteria or poor compliance), and who have completed the required assessments of the primary endpoint as specified in the protocol.
- **Full Analysis Set (FAS):**
The FAS includes all participants who received at least one dose of the study drug and had at least one post-baseline assessment for efficacy endpoints. This set reflects the intention-to-treat principle.
- **Safety Analysis Set:**
The Safety Analysis Set includes all participants who received at least one dose of the study drug and had at least one post-baseline safety assessment. All safety data, including adverse events and rescue medication use, will be analyzed in this set.

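### The per-protocol set leads the analysis of the thermal sensation, comfort and acceptance scales, although membership of that set can depend on how acceptable the sensation was (minor, free to improve)

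*Protocol*

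**What the plan says.** Section 7.4.2 places "Thermal Sensation, Comfort, and Acceptance (ASHRAE Scale" among the secondary endpoints of the efficacy analysis, ahead of the separate safety heading. The test is "Chi-square test or Fisher's exact test for categorical comparisons", with ordinal regression as an optional exploratory addition.

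Section 7.4.1 says that for efficacy the PPS "will be used as the primary analysis set" and that the FAS is secondary. It exempts no endpoint. The PPS excludes major protocol violators, with poor compliance given as an example, and keeps those "who have completed the required assessments of the primary endpoint as specified in the protocol". Section 7.9.1 schedules those assessments: "Inventerisasi Rasa Nyeri Singkat on 1st Visit, 2nd Visit and 3rd Visit". The Safety Analysis Set names adverse events and rescue medication, not the thermal scales.

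Section 5.2 (item 3) says that thermal acceptance "refers to the degree to which a temperature range or condition is considered acceptable or tolerable by individuals". The participant completes Form 8 at all three visits (Section 7.9.2). The first rating follows the supervised first application on Day 0 (Section 7.7.2; the form in Appendix 1 asks about the period after application).

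**The concern.** Acceptance of the sensation is a tolerability-type outcome. The set that leads its analysis is defined by events after randomisation that this outcome can influence. Someone who finds the gel unpleasant may skip home applications or ask to stop. Section 7.8.1 provides for the second case: "When a subject requests for discontinuation (not in relation to AEs". Such a stop need not appear in the adverse event tables. If the sensation is recorded as an adverse event, Section 6.13 allows the dose to be reduced or stopped. Each route can end in poor compliance or missing pain assessments, and so in removal from the PPS.

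That participant already has a Day 0 thermal rating, which the lead analysis would then set aside because of what happened later on another endpoint. The arms also differ in the relevant ingredients: only the test gel lists methyl salicylate, menthol and eugenol (Sections 6.8.1 to 6.8.3).

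A PPS lead can be argued for the pain comparison, which is an equivalence test. That argument does not carry over to scales compared by chi-square or Fisher's exact test with no margin. What is at stake is which of two planned results is read first for a secondary endpoint.

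**Working it through.** The protocol states no figure on this point, so there is nothing to reproduce. The check has two parts: following the text, then gauging how large the effect could be under stated assumptions.

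**Text**

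1. The thermal scales are an efficacy endpoint (Section 7.4.2).
2. Efficacy is led by the PPS, without exception (Section 7.4.1). The missing-data paragraph of Section 7.4.2 repeats the PPS lead for the primary analysis, but does not limit the general rule to the primary endpoint.
3. The PPS depends on compliance and completed pain assessments, both known only after treatment starts.
4. The first thermal rating is given on Day 0, before either can fail.

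So ratings exist that the lead analysis can discard for reasons related to the rating itself. Steps 1, 2 and 4 are stated. That dislike leads to exclusion is an inference.

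**Size, first illustration**

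Inputs: 60 per arm and 10% dropout (Section 6.7), so 60 × 0.10 = 6 leave the PPS in one arm. Assumed: a two-way split into acceptable and unacceptable; true unacceptable rates of 5% (3/60) and 20% (12/60); and k of the 6 leavers having rated the sensation unacceptable, k = 0 to 3.

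Rate in the PPS = (number unacceptable − k) / (60 − 6).

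| k | True 3/60 = 5.0% | Shift (points) | True 12/60 = 20.0% | Shift (points) |
|---|---|---|---|---|
| 0 | 3/54 = 5.6% | +0.6 | 12/54 = 22.2% | +2.2 |
| 1 | 2/54 = 3.7% | −1.3 | 11/54 = 20.4% | +0.4 |
| 2 | 1/54 = 1.9% | −3.1 | 10/54 = 18.5% | −1.5 |
| 3 | 0/54 = 0.0% | −5.0 | 9/54 = 16.7% | −3.3 |

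For scale, the standard error of a between-arm difference at 60 per arm is:

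- at 5%: √(2 × 0.05 × 0.95 / 60) = 4.0 points
- at 20%: √(2 × 0.20 × 0.80 / 60) = 7.3 points

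Seven of the eight shifts are below one standard error. The exception (−5.0) needs every participant with an unacceptable rating to leave.

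**Size, harsher illustration**

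Let u be the true unacceptable share, e_u the exclusion rate among those participants and e_a the rate among the rest. Then

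rate in the PPS = u(1 − e_u) / [u(1 − e_u) + (1 − u)(1 − e_a)].

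With u = 20% and e_a = 5%, all assumed:

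- e_u = 5%: 20.0%, no bias, because exclusion is unrelated to the rating
- e_u = 25%: 0.15 / (0.15 + 0.76) = 16.5%
- e_u = 50%: 0.10 / (0.10 + 0.76) = 11.6%
- e_u = 75%: 0.05 / (0.05 + 0.76) = 6.2%

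Large distortion therefore needs strongly selective exclusion, and nothing in the protocol says that this is expected.

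**The case against.** The other side has a good deal of force.

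- **The alternative result is already planned.** The FAS needs one dose and one post-baseline efficacy assessment. If the thermal scales count as efficacy, the Day 0 rating could itself qualify, and the FAS would then be close to the set proposed here. This stands, and it limits the point to which result leads. Section 7.4.1 does not say whether a rating given on Day 0 after the first dose counts as post-baseline.
- **Nothing formal depends on the order.** The thermal scales have no hypothesis, margin or success criterion. This stands.
- **The route to exclusion is inferred.** No section links acceptance to compliance or withdrawal, and no compliance threshold is given. Treatment lasts about six days with daily reminders and physiotherapist application at each visit. At discontinuation the investigator "performs the observation and tests specified in" the schedule. This stands, and is why the effect is probably small.
- **Safety overlaps.** Symptoms in the diary become safety data (Section 5.2), so a sensation bad enough to cause stopping may be captured there. This holds in part, because withdrawal unrelated to adverse events remains possible.
- **Changing the set cannot recover ratings never given** at visits 2 and 3. This stands, and it shapes the fix.
- **Analysis sets for secondary endpoints often belong in the SAP.** Here, though, the protocol has already fixed the lead set for all efficacy endpoints, so this is a stated choice and not a missing detail.

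A reader might infer that the PPS lead will flatter the test gel. The documents do not support this. They give no rates, and Section 2.1 reports that most patients in an earlier study preferred the warmth and took it as a sign of effect. Comparator participants who feel nothing could equally be the ones to leave. Nor does the point touch the pain equivalence conclusion.

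**Conclusion.** The point holds as a minor one. As written, the protocol leads a tolerability-type outcome with a set whose membership that outcome can influence, although ratings free of that selection are collected on Day 0. The equivalence rationale for a PPS lead does not reach these scales.

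The direction of any bias is unknown and its size is probably small. In the first illustration the shift runs from +0.6 to −5.0 points at a true 5%, and from +2.2 to −3.3 points at a true 20%. In the harsher one, a true 20% can read as low as 6.2%. These ranges rest on assumed rates and a two-way grouping of the acceptance scale; they show what could happen and do not estimate it. If exclusion is unrelated to acceptance, there is no bias.

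**What to change.** Add to Section 7.4.2, or enter in the SAP:

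> Thermal sensation, comfort and acceptance will be analysed primarily, by visit, in all participants who received at least one application and gave a Form 8 rating. The Day 0 rating after the first application is the lead comparison, because it precedes any dropout. Visit 2 and visit 3 ratings will be reported on all available data with the number missing by arm, and remain open to dropout. The PPS analysis is supportive.

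This needs no new data, visits or participants. A protocol change requires sponsor agreement and IRB/EC approval (Sections 7.11.1 and 7.11.2); an SAP entry would also do. One possible downside for the sponsor is that an arm's reported acceptability may look less favourable. Ratings missing at visits 2 and 3 are not recovered, which is why the Day 0 comparison should lead.

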6.7 Sample Size

Assumptions

- Outcome	: Pain score
- Standard deviation (σ)	: 1.81
- Clinically meaningful margin (Δ or δ)	: 1.0
- Power	: 80% ($Z_{1-\beta} = 0.84$)
- Significance level (α)	: 0.05

Reference standard deviation from Kocak AO, Dogruyol S, Akbas I, Menekse TS, Gur STA, Kocak MB, Cekmen B, Orun S, Cakir Z. Comparison of topical capsaicin and topical piroxicam in the treatment of acute trauma-induced pain: A randomized double-blind trial. Am J Emerg Med. 2020 Sep;38(9):1767-1771. doi: 10.1016/j.ajem.2020.05.104. Epub 2020 Jun 2. PMID: 32739846.

For **equivalence trials with 3 groups**, you typically plan for **pairwise equivalence testing**:

- Diclofenac vs. Piroxicam
- Diclofenac vs. PXM plus Counterirritant
- Piroxicam vs. PXM plus Counterirritant

This means you must **adjust α** to account for **multiple comparisons**, commonly using **Bonferroni correction**:

$$\text{Adjusted } \alpha = 0.05 / 3 = 0.0167 \rightarrow Z_{1-\alpha/2} \approx \mathbf{2.39}$$

Sample Size Formula and Calculation

Using the formula for equivalence trials:

$$n = ((Z_{1-\alpha/2} + Z_{1-\beta}) \times \sigma / \Delta)^2$$

Substituting the values:

$$n = ((2.39 + 0.84) \times 1.81 / 1.0)^2$$

$$n = (4.059 \times 1.81)^2 = (7.35)^2 = 54.0$$

Sample size per group (rounded): 54

Total sample size for 3 groups: 162

With 10% dropout:

Total = $162 / (1 - 0.10) \approx 180$ participants

Recommended: 60 participants per group

The clinical study will be recruited in total 180 subjects, which means 60 subjects per arm.

Justification:

- We used the reference from Kocak et al. because: The study used topical piroxicam, which is the main active ingredient in Counterpain PXM. The study was randomized, double-blind, and controlled, and reported the standard deviation of pain scores in full—a parameter that is essential for sample size calculations. To date, we have not found any publications comparing diclofenac gel directly with topical piroxicam, with standard deviations appropriate for use in statistical calculations. So, even though the comparator was capsaicin, this reference was chosen because it is quite representative in terms of pain type and study design.

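### The named test for the thermal scales ignores their order; make the ordinal analysis a planned one for comfort and acceptance, and set it beside chi-square/Fisher for sensation (minor, secondary endpoint)

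*Protocol*

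**What the plan says.** Section 5.2, item 3, makes the thermal ratings a secondary endpoint: "thermal sensation, thermal comfort, and thermal acceptance using ASHRAE 7-point scale questionnaire". For sensation it describes the "ASHRAE 7-point scale, which consists of seven verbal anchors", running in order from cold through neutral to hot. It adds that the result will be the number of thermal sensations felt in relation to the product. Section 7.9.2 has the participant record "thermal sensation, thermal comfort, and thermal acceptance and time of thermal sensation" at each of the three visits.

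Section 7.4.2 labels as the test for all three ratings: "Chi-square test or Fisher's exact test for categorical comparisons". The next line says that ordinal regression "may be used to explore patterns of thermal perception across groups". The general rule is a "level of statistical significance set at $p < 0.05$, unless otherwise adjusted". Section 6.7 fixes the numbers: "The clinical study will be recruited in total 180 subjects, which means 60 subjects per arm", from 54 per group before the 10% dropout allowance. No expected distribution, effect size or power is stated for the thermal ratings.

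**The concern.** A chi-square or Fisher test treats the answers as unordered labels. Shuffling the seven columns of a 3-arm table leaves the p-value unchanged. If one gel moves ratings in one direction, such a test spreads that signal over many degrees of freedom and detects it less often than a method that uses the order. A significant result also carries no direction or effect size.

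This endpoint is a plausible place for the counterirritant gel to differ. Section 2.1 reports that most patients in one 1995 study liked the warm feeling after application. At stake is whether a moderate shift in comfort or acceptance is reported as no difference, although the plan already names a method that would use the order.

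**Working it through.** **Inputs from the protocol.** Three arms; 60 per arm recruited and 54 per arm after dropout (60 × 0.90 = 54); significance level 0.05, taken as two-sided; seven ordered categories for sensation.

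**Plan's own figure.** There is none for this endpoint. The printed pain-score formula with its stated inputs gives ((2.39 + 0.84) × 1.81 / 1.0)² = 34.2, not 54. That is a separate matter: only the planned counts of 54 and 60 are used here.

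**Assumed.** Baseline distributions and effect sizes. One arm is shifted by a common odds ratio (OR) and the other two are equal.

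**Degrees of freedom.** Chi-square on a 3 × 7 table: (3 − 1)(7 − 1) = 12. Rank test (Kruskal-Wallis, the score-type analogue of proportional-odds regression): 3 − 1 = 2.

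**Worked case: equal baseline (1/7 each), OR 2, 60 per arm.**

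1. Baseline cumulative probability is k/7. Shifted, it is k/(k + 2(7 − k)) = k/(14 − k), so the shifted category probabilities are 0.077, 0.090, 0.106, 0.127, 0.156, 0.194 and 0.250.
2. Chi-square noncentrality: n Σ over arms and categories of (p − p̄)²/p̄ = 6.11. On 12 degrees of freedom (critical value 21.03), power is 30%.
3. Rank-test noncentrality: n Σ over arms of (m − m̄)²/v = 6.06, where m is an arm's mean rank score and v the pooled score variance. On 2 degrees of freedom (critical value 5.99), power is 59%.

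The signal is almost the same; the degrees of freedom account for the difference. Simulation of a flat 7-category baseline gave 29.1% and 59.5%.

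**Range by simulation** (2,500 trials per case, three arms, 60 per arm; power in %, chi-square / rank test):

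| Baseline | OR 1.5 | OR 2 | OR 2.5 | OR 3 | OR 4 |
|---|---|---|---|---|---|
| 7 categories, centred | 10 / 21 | 23 / 53 | 45 / 79 | 65 / 92 | 89 / 99 |
| 7 categories, mostly neutral | 6.8 / 16.3 | 16.5 / 43.1 | 33.5 / 69.0 | 48.3 / 82.6 | 78.7 / 96.7 |
| 7 categories, skewed | 10.2 / 22.6 | 26.8 / 56.9 | 50.1 / 81.8 | 70.4 / 94.0 | 92.2 / 99.5 |
| 5 categories | 12.5 / 22.3 | 33.5 / 57.8 | 56.3 / 79.3 | 75.4 / 93.1 | 95.1 / 99.4 |
| 4 categories | 13.5 / 21.2 | 35.8 / 54.5 | 61.4 / 79.9 | 78.0 / 92.4 | 93.6 / 98.6 |

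- **54 per arm:** the gaps are similar. The largest is 26.9% against 63.7%, about 37 points (mostly neutral baseline, OR 2.5).
- **4 or 5 categories:** the gap is about 7 to 25 points for OR 1.5 to 3 and 4 to 5 points at OR 4.
- **Large shifts:** at OR 5 with 54 per arm on the equal 7-category baseline, the step 2 and 3 formulas give 95.4% against 99.7%, a gap of about 4 points.
- **Fisher's exact test:** it behaves like chi-square. On the centred baseline with two arms at OR 2.5 it has 47% power, against 78% for Wilcoxon.
- **Type I error:** about 3 to 5% for chi-square and 4 to 6% for the rank tests, so the gain is not bought with false positives.

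**Where it reverses.** Suppose one gel spreads sensation both ways, with neutral falling symmetrically from 72% to 32%. Chi-square then has about 97% power and Kruskal-Wallis about 6%. For a spread that leans warm the figures are about 98% and 25%.

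**The case against.** The strongest counter-argument concerns sensation, the only scale whose anchors the protocol prints. It is bipolar with neutral in the middle, and a gel containing menthol and methyl salicylate could cool some users and warm others. A location-shift test could miss that almost entirely. Section 5.2 also describes the result as a number of sensations felt, which a comparison of category counts answers directly. This stands: for sensation the nominal test is defensible and should not be demoted.

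A reader might infer that 10 to 35 points are lost on all three ratings. Section 5.2 ties all three to a 7-point questionnaire, but the response images for comfort and acceptance in Appendix 1 are not shown, so their category counts cannot be confirmed. A reader might also infer that a marked warming effect would be missed. It would not: the loss nearly vanishes for large shifts.

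Nor does the plan lack an ordinal method; the question is which method leads. But the line labelled as the test is nominal and the ordinal method is optional, so the choice could be made after the results are seen. Sparse cells are no defect, since Fisher's exact test is offered, and the handling of the three visits may properly be left to a statistical analysis plan.

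**Conclusion.** The point holds as a minor, inexpensive improvement. It is firmest for comfort and acceptance, where direction is the natural question and the named test ignores the order. For sensation the two tests answer different questions and both have a place.

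The size depends on assumed baselines, a common odds ratio and a one-directional shift, because the protocol supplies none of these. A reader might go further and conclude that the equivalence claim is weakened. The documents do not support that: this is one secondary endpoint without a stated power, and the pain score has its own analysis.

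**What to change.** In Section 7.4.2:

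- **Comfort and acceptance:** make proportional-odds ordinal regression (or the equivalent rank test) the planned analysis. Report pairwise odds ratios between gels with 95% confidence intervals, and keep the category table as description.
- **Sensation:** keep chi-square/Fisher as a planned test of equal standing, and pre-specify the ordinal analysis beside it for a directional shift.

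The cost is a line or two of wording, with no new data, visits or participants. The one added task is to check the proportional-odds assumption.
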